10.3.1. Definition of AE

10.3.1.1. AE Definition

- An AE is any untoward medical occurrence in a participant or clinical study participant, temporally associated with the use of study intervention, whether or not considered related to the study intervention.

Note: An AE can therefore be any unfavorable and unintended sign (including an abnormal laboratory finding), symptom, or disease (new or exacerbated) temporally associated with the use of study intervention.

10.3.1.2. Events Meeting the AE Definition

- Any abnormal laboratory test results (hematology, clinical chemistry, or urinalysis) or other safety assessments (e.g., ECG, radiological scans, or vital signs measurements), including those that worsen from baseline, considered clinically significant in the medical and scientific judgment of the investigator (that is, not related to progression of underlying disease).
- Exacerbation of a chronic or intermittent pre-existing condition, including either an increase in frequency and/or intensity of the condition.
- New condition detected or diagnosed after study intervention administration, even though it may have been present before the start of the study.
- Signs, symptoms, or the clinical sequelae of a suspected drug-drug interaction.
- Medication error, misuse, or abuse of IMP, including signs, symptoms, or clinical sequelae.

10.3.1.3. Events Not Meeting the AE Definition

- Any clinically significant abnormal laboratory findings or other abnormal safety assessments which are associated with the underlying disease, unless judged by the investigator to be more severe than expected for the participant's condition.
- The disease/disorder being studied or expected progression, signs, or symptoms of the disease/disorder being studied, unless more severe than expected for the participant's condition.
- Planned surgeries and nonsurgical interventions should not be reported as AEs unless the underlying medical condition has worsened during the course of the study.
- Situations in which an untoward medical occurrence did not occur (social and/or convenience admission to a hospital).

Anticipated day-to-day fluctuations of pre-existing disease(s) or condition(s) present or detected at the start of the study that do not worsen.

10.3.2. Definition of SAE

An SAE is defined as any untoward medical occurrence that, at any dose:

a. Results in Death

b. Is Life-Threatening

- The term 'life-threatening' in the definition of 'serious' refers to an event in which the participant was at risk of death at the time of the event. It does not refer to an event which hypothetically might have caused death if it were more severe.

c. Requires Inpatient Hospitalization or Prolongation of Existing Hospitalization

- In general, hospitalization signifies that the participant has been admitted to the hospital for observation and/or treatment that would not have been appropriate in the physician's office or outpatient setting. Complications that occur during hospitalization are AEs. If a complication prolongs hospitalization or fulfills any other serious criteria, the event is serious. When in doubt as to whether "hospitalization" occurred or was necessary, the AE should be considered serious.
- Hospitalization for elective treatment of a pre-existing condition that did not worsen from baseline of the originating study is not considered an AE.

d. Results in Persistent Disability/Incapacity

- The term disability means a substantial disruption of a person's ability to conduct normal life functions.
- This definition is not intended to include experiences of relatively minor medical significance, such as uncomplicated headache, nausea, vomiting, diarrhea, influenza, and accidental trauma (e.g., sprained ankle), which may interfere with or prevent everyday life functions but do not constitute a substantial disruption.

e. Is a Congenital Anomaly/Birth Defect or Other Abnormal Pregnancy Outcome

Abnormal pregnancy outcomes (for example, spontaneous abortion, fetal death, stillbirth, congenital anomalies, ectopic pregnancy) are considered SAEs.

f. Other Situations:

- Medical or scientific judgment should be exercised in deciding whether SAE reporting is appropriate in other situations, such as important medical events that may not be immediately life-threatening or result in death or hospitalization but may jeopardize the participant or may require medical or surgical intervention to prevent one of the other outcomes listed in the above definition. These events should usually be considered serious.
- Examples of such events include invasive or malignant cancers, intensive treatment in an emergency room or at home for allergic bronchospasm, blood dyscrasias or convulsions that do not result in hospitalization, or development of drug dependency or drug abuse.

10.3.3. Definition of Product Complaints

See Section 8.3.8.

10.3.4. Recording and Follow-Up of AE and/or SAE

10.3.4.1. AE and SAE Recording

- When an AE/SAE occurs, it is the responsibility of the investigator to review all documentation (e.g., hospital progress notes, laboratory reports, and diagnostics reports) related to the event.
- The investigator will then record all relevant AE/SAE information in the CRF.
- It is **not** acceptable for the investigator to send photocopies of the participant's medical records to sponsor or designee in lieu of completion of the AE/SAE CRF page.
- There may be instances when copies of medical records for certain cases are requested by the sponsor or designee. In this case, all participant identifiers, with the exception of the participant number, will be redacted on the copies of the medical records before submission to the sponsor or designee.
- The investigator will attempt to establish a diagnosis of the event based on signs, symptoms, and/or other clinical information. Whenever possible, the diagnosis (not the individual signs/symptoms) will be documented as the AE/SAE.

10.3.4.2. Assessment of Intensity

The investigator will make an assessment of intensity for each AE and SAE reported during the study and assign it to one of the following categories:

- Mild: An event that is easily tolerated by the participant, causing minimal discomfort, and not interfering with everyday activities.
- Moderate: An event that causes sufficient discomfort and interferes with normal everyday activities.
- Severe: An event that prevents normal everyday activities. An AE that is assessed as severe should not be confused with an SAE. Severe is a category utilized for rating the intensity of an event, and both AEs and SAEs can be assessed as severe.
- An event is defined as 'serious' when it meets at least one of the predefined outcomes as described in the definition of an SAE, NOT when it is rated as severe.

10.3.4.3. Assessment of Causality

- The investigator is obligated to assess the relationship between study intervention and each occurrence of each AE/SAE.
- A "reasonable possibility" of a relationship conveys that there are facts, evidence, and/or arguments to suggest a causal relationship, rather than a relationship cannot be ruled out.
- The investigator will use clinical judgment to determine the relationship.
- Alternative causes, such as underlying disease(s), concomitant therapy, and other risk factors, as well as the temporal relationship of the event to study intervention administration will be considered and investigated.
- The investigator will also consult the IB and/or Product Information for marketed products in his/her assessment.
- For each AE/SAE, the investigator **must** document in the medical notes that he/she has reviewed the AE/SAE and has provided an assessment of causality.

- There may be situations in which an SAE has occurred and the investigator has minimal information to include in the initial report to the sponsor or designee. However, it is very important that the investigator always make an assessment of causality for every event before the initial transmission of the SAE data to the sponsor or designee.
- The investigator may change his/her opinion of causality in light of follow-up information and send an SAE follow-up report with the updated causality assessment.
- The causality assessment is one of the criteria used when determining regulatory reporting requirements.

10.3.4.4. Follow-Up of AEs and SAEs

- The investigator is obligated to perform or arrange for the conduct of supplemental measurements and/or evaluations, as medically indicated or as requested by the sponsor or designee, to elucidate the nature and/or causality of the AE or SAE as fully as possible. This may include additional laboratory tests or investigations, histopathological examinations, or consultation with other health care professionals.
- If a participant dies during participation in the study or during a recognized follow-up period, the investigator will provide the sponsor or designee with a copy of any postmortem findings, including histopathology.
- New or updated information will be recorded in the originally completed CRF.
- The investigator will submit any updated SAE data to the sponsor or designee within 24 hours of receipt of the information.

10.3.5. Reporting of SAEs

Note that pregnancies (during maternal or paternal exposure to investigational product) are also reported using the SAE reporting process for tracking purposes (even though pregnancy is not considered an AE/SAE as described in Section 8.3.1). Refer to Section 8.3.4 for regulatory reporting requirements for SAEs.

10.3.5.1. SAE Reporting via an Electronic Data Collection Tool

- The primary mechanism for reporting an SAE will be the electronic data collection tool.
- If the electronic system is unavailable, then the site will use the paper SAE data collection tool (see next section) in order to report the event within 24 hours.
- The site will enter the SAE data into the electronic system as soon as it becomes available.
- After the study is completed at a given site, the electronic data collection tool will be taken offline to prevent the entry of new data or changes to existing data.
- If a site receives a report of a new SAE from a study participant or receives updated data on a previously reported SAE after the electronic data collection tool has been taken offline, then the site can report this information on a paper SAE form (see next section) or to the medical monitor by telephone.
- Contacts for SAE reporting can be found in site training documents.

10.3.5.2. SAE Reporting via Paper CRF

- Facsimile transmission of the SAE paper CRF is the preferred method to transmit this information to the sponsor.
- Initial notification via telephone does not replace the need for the investigator to complete and sign the SAE CRF pages within the designated reporting time frames.

Contacts for SAE reporting can be found in site training documents.

10.4. Appendix 4: Liver Safety: Suggested Actions and Follow-Up Assessments

Hepatic Evaluation Testing

CCI

The Lilly-designated central laboratory should complete the analysis of all selected testing except when testing is required at an increased frequency and a local laboratory must be used for feasibility for the patient (with sponsor approval) CCI, or for testing listed in the investigator-designated local laboratory table. The central laboratory will report results if a validated test or calculation is available.

Notes for the use of local labs:

- The local laboratory must be qualified in accordance with applicable local regulations.
- Site personnel should update documentation per local requirements and sponsor guidance.
- Assay results and reference ranges should be collected and documented as per sponsor guidance.

Local testing may also be performed *in addition to central testing* when necessary for immediate participant management.

Tests assayed by Lilly-designated central laboratory	
Hepatic Hematology Panel	Hepatitis A virus (HAV) testing
Hemoglobin	HAV total antibody
Hematocrit	HAV IgM antibody
Erythrocytes (RBCs - red blood cells)	Hepatitis B virus (HBV) testing
Leukocytes (WBCs - white blood cells)	Hepatitis B surface antigen (HBsAg)
Differential:	Hepatitis B surface antibody (anti-HBs)
Neutrophils, segmented	Hepatitis B core total antibody (anti-HBc)
Lymphocytes	Hepatitis B core IgM antibody
Monocytes	Hepatitis B core IgG antibody
Basophils	HBV DNA ^b
Eosinophils	Hepatitis C virus (HCV) testing
Platelets	HCV antibody
Cell morphology (RBC and WBC)	HCV RNA ^b
Hepatic Clinical Chemistry Panel	Hepatitis D virus (HDV) testing
Total bilirubin	HDV antibody
Direct bilirubin	Hepatitis E virus (HEV) testing
Alkaline phosphatase (ALP)	HEV IgG antibody
Alanine aminotransferase (ALT)	HEV IgM antibody
Aspartate aminotransferase (AST)	HEV RNA ^b

Gamma-glutamyl transferase (GGT)	Anti-nuclear antibody (ANA)
Creatine kinase (CK)	Anti-smooth muscle antibody (ASMA)^a
Hepatic Coagulation Panel	Anti-actin antibody^c
Prothrombin time, INR (PT-INR)	Immunoglobulin IgA (quantitative)
Urine Chemistry	Immunoglobulin IgG (quantitative)
Drug screen	Immunoglobulin IgM (quantitative)
Haptoglobin	Epstein-Barr virus (EBV) testing
	EBV antibody

Tests assayed ONLY by investigator-designated local laboratory

Acetaminophen	Epstein-Barr virus (EBV) testing
Acetaminophen protein adducts	EBV DNA ^b
Alkaline phosphatase isoenzymes	Cytomegalovirus (CMV) testing:
Ceruloplasmin	CMV antibody
Copper	CMV DNA ^b
Ethyl alcohol (EtOH)	Herpes simplex virus (HSV) testing:
	HSV (Type 1 and 2) antibody
	HSV (Type 1 and 2) DNA ^b
	Liver kidney microsomal type 1 (LKM-1)
	Microbiology
Phosphatidylethanol (PEth)	Culture:
Urine Chemistry	Blood
Ethyl glucuronide (EtG)	Urine

^a Not required if anti-actin antibody is tested.

^b Reflex/confirmation dependent on regulatory requirements, testing availability, or both.

^c Not required if anti-smooth muscle antibody (ASMA) is tested.

CCI

10.5. Appendix 5: Risk Factors for Latent Tuberculosis Infection

Risk Factors for LTBI
Household contact or recent exposure to an active case
Birth or residency in a high burden country (>20/100,000)
Residents and employees of high-risk congregate settings, for example, prisons, homelessness, IV drug use

Abbreviations: IV = intravenous; LTBI = latent tuberculosis infection.

Source: Adapted from Horsburgh and Rubin 2011 and Lewinsohn et al. 2017.

Risk Factors for Increased Likelihood of Progression from LTBI to Active TB
Household contact or close contact with an active case
HIV
Radiographic evidence of old, healed TB that was not treated
Silicosis
Treatment with ≥15 mg prednisone (or equivalent) per day
Children <5 years of age
Chronic renal failure
Treatment with an anti-TNF antibody
Poorly controlled diabetes
IV drug use
Weight ≥10% below normal
Smoking

Abbreviations: HIV = human immunodeficiency virus; IV = intravenous; LTBI = latent tuberculosis infection;

TB = tuberculosis; TNF = tumor necrosis factor.

Source: Adapted from Horsburgh and Rubin 2011.

WHO List of High Burden Countries		
Angola	India	Peru
Azerbaijan	Indonesia	Philippines
Bangladesh	Kenya	Russian Federation
Belarus	Kazakhstan	Sierra Leone
Botswana	Democratic People's Republic of Korea	Somalia
Brazil	Kyrgyzstan	South Africa
Cambodia	Lesotho	Swaziland
Cameroon	Liberia	Tajikistan
Central African Republic	Malawi	United Republic of Tanzania
Chad	Republic of Moldova	Thailand
China	Mozambique	Uganda
Congo	Myanmar	Ukraine
Democratic Republic of the Congo	Namibia	Uzbekistan
Ethiopia	Nigeria	Vietnam
Ghana	Pakistan	Zambia
Guinea-Bissau	Papua New Guinea	Zimbabwe

Abbreviation: WHO = World Health Organization.

Source: WHO 2015.

10.6. Appendix 6: Examples of Infections that May Be Considered Opportunistic in the Setting of Biologic Therapy

This table is provided to aid the investigator in recognizing infections that may be considered opportunistic in the context of biologic therapy, for the purposes of exclusion criteria. This list is not exhaustive. Investigators should use their own clinical judgement in determining if other infections may be considered opportunistic for the purposes of exclusion criteria. Winthrop et al. (2015) consider TB and non-TB mycobacterial disease to be opportunistic infections in the context of biologic therapy.

Bacterial
Bartonellosis (disseminated disease only)
Campylobacteriosis (invasive disease only)
Legionellosis
Listeriosis (invasive disease only)
Nocardiosis
TB
Non-TB mycobacterial disease
Salmonellosis (invasive disease only)
Shigellosis (invasive disease only)
Vibriosis (invasive disease due to Vibrio vulnificus)
Viral
BK virus disease including polyomavirus-associated nephropathy
Cytomegalovirus disease
HBV reactivation
HCV progression
Herpes simplex (invasive disease only)
Herpes zoster (any form)
Posttransplant lymphoproliferative disorder (Epstein-Barr virus)
PML, JC virus
Fungal
Aspergillosis (invasive disease only)
Blastomycosis
Candidiasis (invasive disease or oropharyngeal, esophageal. Not isolated lingual)
Coccidioidomycosis
Cryptococcosis
Histoplasmosis
Paracoccidioides infections
Penicilliosis
Pneumocystosis
Sporotrichosis
Other invasive molds: Mucormycosis (zygomycosis) (Rhizopus , Mucor , and Lichtheimia), Scedosporium/Pseudallescheria boydii , Fusarium

Parasitic
Leishmaniasis (visceral only)
Strongyloidosis (hyperinfection syndrome or disseminated disease)
Microsporidiosis
Toxoplasmosis
Trypanosoma cruzi infection (Chagas' disease progression) (disseminated disease only)
Cryptosporidiosis (chronic disease only)

Abbreviations: HBV = hepatitis B virus; HCV = hepatitis C virus; JC = John Cunningham;

PML = progressive multifocal leukoencephalopathy; TB = tuberculosis.

Source: Adapted from Winthrop et al. 2015.

10.7. Appendix 7: Prohibited Medications

This section outlines medications that are prohibited during both the originator studies and the AMAX study. Use of the medications listed in this appendix is allowed at the discretion of the investigator after a participant discontinues study drug and completes the ETV.

Drug Class	Guidance for Use
The following medications are prohibited throughout duration of study:	
Anti-TNF antibodies (for example, infliximab, adalimumab, or certolizumab pegol)	Prohibited throughout duration of study.
Anti-integrin antibodies:	
Natalizumab	Prohibited throughout duration of study.
Other anti-integrin antibodies (for example, vedolizumab)	Prohibited throughout duration of study.
Agents depleting B or T cells (for example, rituximab, alemtuzumab, or visilizumab)	Prohibited throughout duration of study.
Immunomodulatory medications, including oral cyclosporine, IV cyclosporine, tacrolimus, mycophenolate mofetil, thalidomide, or JAK inhibitors (other than topical)	Prohibited throughout duration of study.
Rectally administered 5-ASA therapies (enemas or suppositories)	Prohibited throughout duration of study.
Rectally administered corticosteroids (enemas or suppositories)	Prohibited throughout duration of study.
Corticosteroids	
A course of IV corticosteroids is prohibited throughout duration of study, except for use as premedication for infusion or for short-term treatment of acute non-CD events (for example, allergic reactions). IV corticosteroids used for CD may result in discontinuation, therefore consult your medical monitor.
 
From Week 0 to Week 12, initiation or adjustment of systemic corticosteroids for non-CD indications is prohibited unless needed due to AEs or for appropriate medical management.
 
After Week 12, participants may transiently initiate or increase doses (that is, for <4 weeks) of corticosteroids for reasons other than loss of response to treatment for CD (for example, premedication for infusions, and stress doses of corticosteroids for surgery, asthma, and allergic reaction).
 
Locally administered corticosteroids (for example, inhaled, intranasal, intra-articular, or topical) are allowed.
 
Systemic corticosteroid use is allowed for adrenocortical insufficiency (Section 6.5 and 6.7.1).

Any investigational therapy (biologic or nonbiologic)	Prohibited throughout duration of study.
Interferon therapy	Prohibited unless medically necessary for short-term COVID treatment

Drug Class	Guidance for Use
Leukocyte apheresis (leukapheresis, for example, Adacolumn)	Prohibited throughout duration of study.
Anti-IL-23p19 antibodies (for example, risankizumab [BI-655066], brazikumab [MEDI-2070], guselkumab [CANTO1959], or tildrakizumab [MK-3222]) for any indication, including investigational use	Prohibited throughout duration of study.
Anti-IL 12/23p40 antibodies (for example, ustekinumab)	Prohibited throughout duration of study.
BCG vaccine	BCG vaccination prohibited throughout the duration of the study and for 12 months after discontinuation of study drug.
Live attenuated vaccines	Live attenuated vaccines are prohibited throughout the duration of the study and for 3 months after discontinuation of study drug.
Medicinal and recreational marijuana (includes CBD Oil)	Marijuana use is prohibited through the end of the long-term extension period of the study. If use is identified prior to this time, it may result in discontinuation, consult the medical monitor.

Abbreviations: 5-ASA = 5-aminosalicylic acid; AE = adverse event; BCG = Bacillus Calmette Guerin; CBD = cannabidiol; CD = Crohn's disease; COVID = coronavirus disease; IL = interleukin; IM = intramuscular; IV = intravenous; JAK = Janus kinase; TNF = tumor necrosis factor.

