6.5.2. Prohibited Therapy

Use of prohibited medications should not be withheld if, in the opinion of the investigator, failure to prescribe them would compromise participant safety. Participants who require a prohibited medication should be discontinued from study drug as described in Section 7.1.2 and should complete an early termination visit (ETV) and posttreatment follow-up visits as described in the SoA (Section 1.3). Some exceptions (IV corticosteroid, systemic corticosteroids for non-CD indications, and marijuana) may not necessarily result in discontinuation. Consult the medical monitor prior to discontinuing the participant (see Section 10.7, Appendix 7).

If a concomitant medication is needed to treat an AE or for appropriate medical management, the investigator should base decisions on the participant and clinical factors, considering the list of prohibited medication.

Vaccinations

Use of BCG vaccination is prohibited throughout the duration of the study and for 12 months after discontinuation of study drug.

Use of live, attenuated vaccines are prohibited during the study and for 3 months after discontinuation of study drug.

Use of nonlive (killed, inactivated, subunit, and RNA-based) vaccinations are allowed; however, their efficacy with concomitant mirikizumab is unknown.

For More Information

The list of prohibited medications is provided in Section 10.7, Appendix 7.

The list of permitted medications with dose stabilization guidance is provided in Section 10.8, Appendix 8.

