7.1. Discontinuation of Study Intervention

Study drug may be permanently discontinued or temporarily withheld during the study.

Participants who permanently discontinue study drug early will undergo ET procedures, which include:

- an ETV, and
- posttreatment follow-up visits (Visit 801 and Visit 802).

The investigator will complete any AE reporting and necessary follow-up (Section 8.3).

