10.13.10.2. Prohibited Concomitant Medications/Therapies during Continued Access

This section outlines medications that, if initiated, require treatment and study discontinuation (Section 10.13.8) during the AMAX Continued Access Period, if applicable. If there are any questions on medications, please contact the medical monitor.

Drug Class (examples)	Continued Access Period Comments and Guidelines
IV corticosteroids for CD	Course of IV corticosteroids prohibited
Systemic corticosteroids for non-CD indication, oral or IV Allowed exceptions: See Section 10.13.10.1	Prohibited
Immunomodulatory medications, oral or IV: Cyclosporine, mycophenolate mofetil, thalidomide, tacrolimus Other immunomodulatory medications should be discussed with medical monitor prior to use	Prohibited
Agents depleting B or T cells (alemtuzumab, rituximab, visilizumab)	Prohibited
Interferon therapy	Prohibited unless medically necessary for short term COVID treatment
Leukocyte apheresis, leukapheresis (Adacolumn)	Prohibited
Bacillus Calmette-Guerin (BCG) vaccination	Use prohibited during study and \leq 12M after last dose of mirikizumab
Live or attenuated vaccines (for measles, mumps, rubella, or varicella)	Use prohibited during study and \leq 3M after last dose of mirikizumab

Abbreviations: CD = Crohn's disease; COVID = coronavirus disease; IV = intravenous; M = month.

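### Appendix 7's general permission after the early termination visit conflicts with the 12-month BCG and 3-month live-vaccine bars in its own table and in Section 6.5.2

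*Protocol*

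**What the plan says.** Protocol Appendix 7 (Section 10.7) opens with two sentences. The first describes the content: "This section outlines medications that are prohibited during both the originator studies and the AMAX study". The second lifts the prohibition for people who have stopped treatment, saying that taking "medications listed in this appendix is allowed at the discretion of the investigator after a participant discontinues study drug and completes the ETV". It names no exception.

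Two rows of the table beneath concern vaccines:

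- The first of these rows: "BCG vaccination prohibited throughout the duration of the study and for 12 months after discontinuation of study drug".
- The second of these rows: "Live attenuated vaccines are prohibited throughout the duration of the study and for 3 months after discontinuation of study drug".

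Section 6.5.2, under its Vaccinations heading, gives the same rules: "Use of BCG vaccination is prohibited throughout the duration of the study and for 12 months after discontinuation of study drug" and "Use of live, attenuated vaccines are prohibited during the study and for 3 months after discontinuation of study drug". It then refers the reader to Appendix 7 for the full list.

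Section 7.1 fixes who has an early termination visit (ETV): "Participants who permanently discontinue study drug early will undergo ET procedures", consisting of the ETV itself and post-treatment Visits 801 and 802.

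**The concern.** The permission and the two vaccine bars both turn on the participant stopping study drug. Once the ETV is done, the permission is in force, and the vaccine bars are still running. For the remainder of the 12 or 3 months an investigator has two instructions that cannot both be followed as written.

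The stake is participant safety and protocol compliance. The sponsor evidently wants these vaccines withheld for a defined time after mirikizumab: exclusion criterion 20 keeps out anyone intending to receive them during the study, and the post-treatment periods extend the same caution. An investigator who withholds the vaccine complies with every statement. One who relies on the introductory sentence breaches both the row and Section 6.5.2.

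**Working it through.** There is no figure to reproduce. The check is a comparison of text and a count of rows.

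**Text side by side, for an early discontinuer after the ETV**

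| Place in protocol | BCG | Live attenuated vaccines |
|---|---|---|
| Appendix 7, second sentence | Investigator's discretion | Investigator's discretion |
| Appendix 7, table row | Barred for 12 months after stopping | Barred for 3 months after stopping |
| Section 6.5.2 | Barred for 12 months after stopping | Barred for 3 months after stopping |

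The vaccine rows stand under the table's heading for prohibited medications, so the general sentence covers them as worded.

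**Length of the conflict.** It runs from the ETV to the end of the barred period, that is, the barred period minus the time from stopping drug to the ETV. If the ETV falls on the day of stopping, the conflict lasts the full 12 or 3 months; any delay shortens it by the same amount.

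**How many rows are involved.** Counting rows of Appendix 7 that carry their own guidance text:

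- 11 rows say only that the treatment is prohibited for the duration of the study: anti-TNF, natalizumab, other anti-integrins, B- or T-cell depleting agents, immunomodulatory drugs, rectal 5-ASA, rectal corticosteroids, investigational therapy, leukocyte apheresis, anti-IL-23p19 and anti-IL-12/23p40.
- 3 rows have other guidance but no period after stopping: corticosteroids, interferon and marijuana.
- 2 rows set a period counted from stopping study drug: BCG and live attenuated vaccines.

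Total: 11 + 3 + 2 = 16 rows. Rows that conflict: 2. Rows that do not: 16 − 2 = 14.

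**Comparison with Continued Access.** Section 10.13.10.3 attaches its permission after stopping mirikizumab to a separate table of seven examples of Crohn's treatment, none of them a vaccine. The vaccines stay in the prohibited table of Section 10.13.10.2 with their own limits, for example "12M after last dose of mirikizumab" for BCG. The main appendix does not separate the two.

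**The case against.** The strongest reply is that the text can be read as consistent. A specific row normally prevails over a general introduction. The vaccine rows have a part that operates only after study drug stops, and that part would be pointless for early discontinuers if the introduction cancelled it. Every specific statement about these vaccines agrees on the length of the bar. The sentence is also merely permissive, and an investigator would have to disregard both the row and Section 6.5.2 to go wrong.

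Much of this stands. The specific-over-general reading is the likely one, and the practical risk is small. It does not remove the conflict, for three reasons. First, the protocol states no order of precedence. Second, the introductory sentence works by overriding row text: early discontinuers still have Visits 801 and 802 after the ETV, so for the 11 rows barring use throughout the study, the sentence has effect during follow-up only if it prevails over the row. The reader must let it prevail over those rows but not over these two, with nothing in it to say so. Third, the vaccine rows' post-treatment periods would still apply to participants who complete treatment without an ETV, so they would not be empty even if the sentence did override them for early discontinuers.

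A related objection is that, read literally, those 11 rows would also clash with the sentence. They differ in kind: they state an in-study bar, which the sentence is evidently meant to lift, whereas the vaccine rows set an explicit period counted from stopping drug. The count of 2 rests on that distinction.

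**Conclusion.** The contradiction is real and sits in current, unredacted text. It is confined to 2 of the 16 guidance rows of Appendix 7 and to participants who stop study drug early and complete the ETV. The documents do not give the number of such participants, and none is estimated here. The conclusion assumes that the introductory sentence is intended to lift the in-study bars after the ETV, so that the other 14 rows are not in conflict with it. Endpoints, analysis sets and statistical methods are unaffected. The point is minor in scale, but a safety instruction should not depend on the reader guessing which of two statements governs, so it should be corrected.

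**What to change.** Leave the first sentence of Appendix 7 as it is. At the end of the second, add: *except BCG and live attenuated vaccines, which remain prohibited for 12 months and 3 months, respectively, after discontinuation of study drug*. Both periods and their starting point are already in the table rows and in Section 6.5.2, so no new clinical decision is needed, and the permission for the other 14 rows is untouched.

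The cost is one clause. Visits, data collection and analysis do not change. Because it alters protocol text, it is best carried in the next amendment opened for other reasons, under the approval rules in Section 10.1.1.
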